APPENDIX D

Food and Medications to Avoid During Your Participation in the Study

Do not consume grapefruit products (grapefruit, grapefruit juice, grapefruit seed extract, or dietary supplements containing grapefruit) while you are participating in the study. You should not use oral formulations (i.e., tablets or capsules) of any of the following medications while you are participating in the study. Topical formulations, including creams, shampoos, foams, and gels applied to the skin, are acceptable. Tell your study doctor immediately if you use any of these medications, or if any of these medications or any new medications are prescribed for you during the study.

Generic name	Brand name(s)		
amiodarone	Pacerone, Cordarone		
amlodipine	Lotrel, Norvasc		
bosentan	Tracleer		
boceprevir	Victrelis		
carbamazepine	Tegretol		
clarithromycin	Biaxin, Prevpac		
cobicistat-containing medications	Evotaz, Genvoya, Prezcobix, Stribild		
colchicine	Colcrys		
cyclosporine	Gengraf, Neoral, Sandimmune		
danazol	Danocrine		
diltiazem	Cardizem, Dilacor, Taztia, Tiazac		
dronedarone	Multaq		
efavirenz	Sustiva, Stocrin		
etravirine	Intelence		
erythromycin	EES, Erythrocin, Ery-Tab, E-Mycin		
gemfibrozil	Lopid		
itraconazole	Onmel, Sporanox		
ketoconazole	Nizoral		
lomitapide	Juxtapid		
modafinil	Provigil		
nafcillin	Nallpen, Unipen		
nefazodone	Serzone		
phenytoin	Dilantin		
posaconazole	Noxafil, Posanol		
ranolazine	Ranexa		
red yeast rice	Over-the-counter supplement, various brands		
rifampin	Rifadin		
St. John's wort (Hypericum perforatum)	Over-the-counter herbal remedy, various		
	brands		
telaprevir telithan ann air	Incivek		
telithromycin	Ketek		
verapamil	Calan, Covera, Isoptin, Verelan		
voriconazole	Vfend		

HIV protease inhibitors (atazanavir, darunavir, fosamprenavir, indinavir, lopinavir, nelfinavir, ritonavir, saquinavir, tipranavir)

Aptivus, Crixivan, Invirase, Kaletra, Lexiva, Norvir, Prezista, Reyataz, Viracept

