4.2 Exclusion Criteria

4.2.1 Prior or current use of statin medication

4.2.2 Current systemic use of medications known to interact with statins and potentially increase toxicity, including gemfibrozil, cyclosporine, danazol, lomitapide, verapamil, diltiazem, dronedarone, amiodarone, amlodipine, ranolazine, strong CYP3A4 inhibitors (e.g., itraconazole, ketoconazole, posaconazole, voriconazole, HIV protease inhibitors, boceprevir, telaprevir, erythromycin, clarithromycin, telithromycin, nefazodone, or cobicistat-containing products), or strong CYP3A4 inducers (e.g., carbamazepine, phenytoin, rifampin, St. John's wort, bosentan, efavirenz, etravirine, modafinil, nafcillin)

4.2.3 History of adverse effects, intolerance, or allergic reactions attributed to compounds of similar chemical or biologic composition to simvastatin (i.e., other statin medications)

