5.4 Contraindications

Patients are advised not to consume any form of grapefruit (e.g., juice, fruit, grapefruit seed extract, dietary supplements containing grapefruit) while on simvastatin as grapefruit may increase the blood levels of simvastatin [114]. Participants enrolled in the study will be instructed to avoid all forms of grapefruit.

The combined use of simvastatin with systemic formulations of gemfibrozil, cyclosporine, danazol, lomitapide, verapamil, diltiazem, dronedarone, amiodarone, amlodipine, ranolazine, or strong CYP3A4 inhibitors (e.g., itraconazole, ketoconazole, posaconazole, voriconazole, HIV protease inhibitors, boceprevir, telaprevir, erythromycin, clarithromycin, telithromycin, nefazodone, and cobicistat-containing products) is contraindicated due to an increased risk for myopathy. Patients will be screened for contraindications to simvastatin prior to enrollment in the study. Patients with known active infection with HIV will be excluded from the study. Patients will be advised not to use contraindicated medications during the study and will be reviewed at study visits and during follow-up telephone calls. Participants will be closely monitored for symptoms and side effects to the study drug and will be instructed to call the study doctor immediately if they have a serious adverse reaction.

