5.5 Concomitant Medications

All medications (prescription and over-the-counter), vitamin and mineral supplements, and/or herbs taken by the participant will be documented on the concomitant medication CRF and will include: 1) start and stop date, dose and route of administration, and indication. Medications taken for a procedure (*e.g.*, biopsy) should also be included.

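### Appendix D tells participants to avoid only tablets and capsules of the listed drugs, but section 5.4 contraindicates systemic formulations of 22 of them during the study

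*Combined protocol and SAP*

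**What the plan says.** Sections 4.4 and 7.2.2 have Appendix D given to every participant who signs consent. After a warning about grapefruit, the sheet states its rule on drugs: "You should not use oral formulations (i.e., tablets or capsules) of any of the following medications while you are participating in the study". The next sentence reads "Topical formulations, including creams, shampoos, foams, and gels applied to the skin, are acceptable". The one after that says "Tell your study doctor immediately if you use any of these medications, or if any of these medications or any new medications are prescribed".

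Section 5.4 sets the rule for the treatment period by formulation: "The combined use of simvastatin with systemic formulations of gemfibrozil, cyclosporine, danazol, lomitapide", followed by further named drugs and the strong CYP3A4 inhibitors, "is contraindicated due to an increased risk for myopathy". It adds: "Patients will be advised not to use contraindicated medications during the study and will be reviewed at study visits and during follow-up telephone calls".

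Exclusion criterion 4.2.2 also works by systemic exposure: "Current systemic use of medications known to interact with statins and potentially increase toxicity, including gemfibrozil, cyclosporine, danazol", then the rest of its list, which includes strong CYP3A4 inducers that 5.4 does not name.

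**The concern.** The sheet is the written list that participants take away at consent, and they may consult it when another clinician treats them during the six months. Its avoid sentence defines the barred forms as tablets or capsules, while the protocol's rule turns on systemic exposure. A participant given a listed drug as an oral liquid or by injection could read the sheet exactly and conclude that the prohibition does not apply.

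What is at stake is myopathy, the reason section 5.4 gives for the contraindication. Sections 5.6 and 7.6 provide for CPK at Study Visit 1 and again only if the participant reports unexplained muscle pain or weakness. Scheduled CPK testing would therefore not reveal an interaction that nobody had reported. This is a safety-wording matter and does not touch the statistical design.

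**Working it through.** No formula applies. The check is a comparison of wording and a count of list entries.

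**Which forms each text covers**

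| Form of a listed drug | Appendix D avoid sentence | Section 5.4 (the drugs it names) |
|---|---|---|
| Tablet or capsule | barred | contraindicated |
| Oral liquid | not mentioned | contraindicated (systemic) |
| Injection or infusion | not mentioned | contraindicated (systemic) |
| Topical on the skin | acceptable | outside the rule |

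The middle two rows are the gap. The sheet introduces tablets and capsules as the definition of oral formulations, not as examples, so liquids fall outside it. Injections would fall outside it on either reading.

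**Which drugs the gap concerns.** HIV protease inhibitors and cobicistat-containing products each count as one entry.

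- Section 5.4: 10 individual drugs + 12 named strong CYP3A4 inhibitors = 22.
- Section 4.2.2: the same 22 + 9 CYP3A4 inducers = 31.
- Appendix D: 33 entries. All 31 in 4.2.2 are present, and 33 − 31 = 2 extras (colchicine and red yeast rice).

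Section 4.2.2 concerns current use and is applied when eligibility is assessed. The contraindication with simvastatin on study is 5.4, which names 22 entries. For the other 33 − 22 = 11 entries (9 inducers and 2 extras), the sheet bars drugs that 5.4 does not name, so it cannot be narrower than 5.4 there. The on-study mismatch therefore concerns 22 entries at most.

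**What happens if one of the 22 is taken anyway**

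- Section 5.6 stops the intervention if any of 7 is started: lomitapide, verapamil, diltiazem, dronedarone, amiodarone, amlodipine or ranolazine. It sets no limit by route.
- Section 6.2 requires simvastatin to be suspended when short-term treatment with a strong CYP3A4 inhibitor cannot be avoided. It names the same 12 inhibitors as 5.4, again with no limit by route.
- These cover 7 + 12 = 19 of the 22. The other 22 − 19 = 3 (gemfibrozil, cyclosporine and danazol) have no specific rule in 5.6 or 6.2, although 8.3 lists concomitant medication as a reason to stop the agent.

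These rules work only once staff know of the drug. The disclosure sentence in Appendix D, the reviews at visits and the medication review on the calls (section 7.3.3, every four weeks ± 7 days) supply that knowledge.

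**The case against.** The strongest reply is that participants are protected by more than this one sentence. The sheet's title speaks of medications to avoid, and only topical products are declared acceptable, so nothing on it permits a liquid or an injection. The disclosure instruction covers any listed drug and any new prescription, whatever the route. Section 5.4 separately promises advice against contraindicated medications, and the consent form, which was not available to me, may carry it. The protocol's on-study handling also includes detecting use and then stopping or suspending simvastatin, and immediate disclosure serves exactly that.

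Most of this stands, and it is why the point is minor. It does not make the avoid sentence right. Disclosure can follow exposure, whereas an instruction not to use the drug comes before it.

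Two further objections also stand. No section says that any listed drug comes as a liquid or an injection. Section 5.5 does have "start and stop date, dose and route of administration, and indication" recorded, but for every medication, vitamin and herb, so it shows nothing about the forms these drugs take.

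A reader might infer that the gap covers everything on the sheet, or all 31 entries in 4.2.2. The documents do not support that: 4.2.2 governs entry, and 5.4 names only 22. A reader might also see a fault in colchicine and red yeast rice being on the sheet but not named in 4.2.2. That is not a defect. The list in 4.2.2 is open-ended, and the extra entries err on the safe side.

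**Conclusion.** The point holds as a minor safety-wording error. For the 22 drugs or classes that section 5.4 contraindicates, the avoid sentence in Appendix D is narrower than the protocol's rule. It leaves oral liquids, injections and infusions neither barred nor permitted.

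The conclusion that this matters in practice rests on the assumption that at least some of the 22 come in such forms. The figure of 22 counts list entries and says nothing about exposures. The documents give no frequency of use, so the number of participants affected could be anywhere from none upward. It is probably small.

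It would go too far to infer that participants are left unprotected, or that the sheet allows these forms. Route-free disclosure, repeated medication review and the rules in 5.6 and 6.2 argue against that. Sample size, power, alpha and the primary analysis are unaffected.

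**What to change.** In Appendix D, replace the phrase that limits the prohibition to tablets and capsules with *any systemic form (tablet, capsule, liquid, injection or infusion)*. Keep the topical exemption and the disclosure sentence as they are. The drug list and section 4.2.2 need no change.

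The cost is a protocol amendment, CIRB approval and reissue of the sheet, including a Spanish version if the sheet is among the translated materials. The change does not need an amendment of its own and can be bundled with the next one.

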APPENDIX E

Clinical Laboratory Minimum Test Requirements

Clinical labs will be done at Screen 1 to confirm eligibility for the trial; and at Study Visits 1, 2, 3, and 4 to monitor for potential adverse effects of the intervention. Labs must include at least the following tests. It is acceptable to do additional tests if they are included in the blood panels at your institution.

Blood Hematology: Complete Blood Count and Differential	Blood Chemistry: Comprehensive Metabolic Panel	Lipid Panel *	Other Blood Tests
Hemoglobin Platelet count Leukocytes (White blood cell count, total) Neutrophil count, absolute	Alanine aminotransferase (ALT (SGPT)) Aspartate aminotransferase (AST (SGOT)) Alkaline phosphatase (ALP) Bilirubin, total Creatinine Sodium Glucose Potassium Total Protein	Total cholesterol High density lipoprotein (HDL) cholesterol Low density lipoprotein (LDL) cholesterol Triglycerides	Hemoglobin A1C (HbA1C) * Prothrombin Time (PT/INR) † Creatine phosphokinase (CPK) §

* Lipid panel and hemoglobin A1C will be done at Study Visits 1, 3, and 4.

[†] Prothrombin Time will be done at Screen 1 and Study Visit 4 to calculate the MELD score.

§ Creatine phosphokinase (CPK) will be measured at Study Visit 1 to establish a patient-specific reference for this indicator of muscle toxicity. If the patient reports unexplained muscle pain or weakness during the trial, CPK will be tested again to check for elevation.

APPENDIX F

Participant ID:	
Date:	

Statin Therapy to Reduce Disease Progression from Liver Cirrhosis to Cancer

Risk Questionnaire

We appreciate the time you are taking to complete this interview. We will be asking you questions about factors and behaviors that we believe may be related to the development of liver cancer. Please try to answer each question as completely as you can, even if you are unsure about the answer. All answers will be kept confidential.

DEMOGRAPHICS

	The next questions ask	about your pers	onal background.		
1.	Were you born in the United States? ¹ <> a. Where were you born? (Show I b. Do you currently live in the Uni <> c. In what ye	ist of Countries an ted States? 1	nd U.S. territories) Yes ° No		
2.	 Where was your biological mother born? ¹ In the United States ² Outside of the United States ⁹ Don't know < Countries (States >> a. Where was she born? (Show list of Countries) 				
3.	Where was your biological father born? ¹ In the United States ² Outside of the <<if of="" outside="" states="" the="" united="">></if> a. Where				
4.	What is your racial background? Check all boxe 1 White or Caucasian 10 2 African-American or Black 11 3 Chinese or Taiwanese 12 4 Filipino 13 5 Japanese or Okinawan 14 6 Korean 15 7 Vietnamese 16 8 Asian Indian 17 9 Other Asian 18] American Indian] Native Hawaiian] Samoan	ander		
5.	 Are you of Hispanic or Latino/a ancestry? Yes, Mexican, Mexican American, Chicano Yes, Other Hispanic	$ _ ∘ □ No → If$ naire for Hispani nd speak? Both equally ³ □	NO skip to question # 6 (educ c acculturation, English or Sp	cation) anish>>	
	c. In what language do you usually think? Only English More English than Spanish	Both equally	More Spanish than English	Only Spanish	
	d. What language do you usually speak with y Only English More English than Spanish	our friends? Both equally ³	More Spanish than English	Only Spanish	

6. What is the highest grade or level of schooling you have completed? Check one box only.
¹ No formal education ⁵ Technical or vocational school
² 8th grade or less ⁶ Associate degree or some college
³ Some high school (9th -11th grade) ⁷ Bachelor's degree
⁴ High school graduate or GED ⁸ Advanced degree (Master's or Doctoral degree)
 7. Are you currently employed (including self-employed)? ¹ □ Yes ⁰ □ No
a. On average, how many hours do you work each week? Check one box only. 1 1-29 hours 2 30-44 hours 3 45-54 hours 4 55+ hours
 8. What is your current marital status? Check one box only. ¹ Single (never married) ² Married ³ Living with partner ⁴ Separated ⁵ Divorced ⁶ Widowed
 9. With whom do you currently live? Check all boxes that apply. ¹ Spouse/partner ² Children ³ Parent(s) ⁴ Parent(s)-in-law ⁵ Other relative(s) ⁶ Friend(s) ⁷ I live alone ⁸ Other (please describe)
10. Excluding you, how many people live in your home who are age If none enter 0.
over 18 years old between 12–18 years old between 6–11 years old under 6 years old
11. Are you covered by health insurance or a health care plan?
\bigcap^{1} Yes \circ No \rightarrow If NO skip to next section – SLEEP
\mathfrak{S}_a . What type of health insurance or health care plan are you enrolled in? Check all boxes that apply.
¹ Employer group insurance through my job or my partner's job ² Self-employed health plan
³ Medicaid/Medi-Cal or other government program ⁴ Medicare
⁵ Private health insurance that I pay for myself ⁶ Military health care
⁷ I have health insurance, but I don't know what type
[®] Other health insurance plan (please describe)

SLEEP

<< SLEEP-50 Questionnaire (selected subscales) >>

The following questions ask about your sleep habits.

Please respond to what extent each of the following statements has been applicable to you during the past 4 weeks.

During the past 4 weeks:	Not at all	Somewhat	Rather much	Very much
1. I am told that I snore.	1	2	3	4
2. I sweat during the night.	1	2	3	4
3. I am told that I hold my breath when sleeping.	1	2	3	4
4. I am told that I wake up gasping for air.	1	2	3	4
5. I wake up with a dry mouth.	1	2	3	4
I wake up during the night while coughing or being short of breath.	1	2	3	4
7. I wake up with a sour taste in my mouth.	1	2	3	4
8. I wake up with a headache.	1	2	3	4
9. I would rather go to bed at a different time.	1	2	3	4
 I go to bed at very different times (more than 2-hour difference). 	1	2	3	4
11. I do shift work.	1	2	3	4
12. I feel tired at getting up.	1	2	3	4
13. I feel sleepy during the day and struggle to remain alert.	1	2	3	4
14. I would like to have more energy during the day.	1	2	3	4
15. I am told that I am easily irritated.	1	2	3	4
16. I have difficulty in concentrating at work or school.	1	2	3	4
17. I worry whether I sleep enough.	1	2	3	4
18. Generally, I sleep badly.	1	2	3	4

19. On a scale of 1 to 10 where 1 is very bad and 10 is very good, how would you rate your sleep?

20. I sleep _____ hours, mostly from (times of day or night) _____ to _____.

DISEASE SPECIFIC QUALITY OF LIFE CHRONIC LIVER DISEASE QUESTIONNAIRE (CLDQ)

These questions are designed to find out how you have been feeling **during the last two weeks**. You will be asked about your symptoms related to your liver disease, how you have been affected in doing activities, and how your mood has been. *Please select only one response for each question*.

		All of the time	Most of the time	A good bit of the time	Some of the time	A little of the time	Hardly any of the time	None of the time
1.	How much of the time during the last two weeks have you been troubled by a feeling of abdominal bloating?	1	2	3	4	5	6	7
2.	How much of the time have you been tired or fatigued during the last two weeks?	1	2	3	4	5	6	7
3.	How much of the time during the last two weeks have you experienced bodily pain?	1	2	3	4	5	6	7
4.	How often during the last two weeks have you felt sleepy during the day?	1	2	3	4	5	6	7
5.	How much of the time during the last two weeks have you experienced abdominal pain?	1	2	3	4	5	6	7
6.	How much of the time during the last two weeks has shortness of breath been a problem for you in your daily activities?	1	2	3	4	5	6	7
7.	How much of the time during the last two weeks have you not been able to eat as much as you would like?	1	2	3	4	5	6	7
8.	How much of the time in the last two weeks have you been bothered by having decreased strength?	1	2	3	4	5	6	7
9.	How often during the last two weeks have you had trouble lifting or carrying heavy objects?	1	2	3	4	5	6	7
10.	How often during the last two weeks have you felt anxious?	1	2	3	4	5	6	7
11.	How often during the last two weeks have you felt a decreased level of energy?	1	2	3	4	5	6	7
12.	How much of the time during the last two weeks have you felt unhappy?	1	2	3	4	5	6	7
13.	How often during the last two weeks have you felt drowsy?	1	2	3	4	5	6	7
14.	How much of the time during the last two weeks have you been bothered by a limitation of your diet?	1	2	3	4	5	6	7
15.	How often during the last two weeks have you been irritable?	1	2	3	4	5	6	7

		All of the time	Most of the time	A good bit of the time	Some of the time	A little of the time	Hardly any of the time	None of the time
16.	How much of the time during the last two weeks have you had difficulty sleeping at night?	1	2	3	4	5	6	7
17.	How much of the time during the last two weeks have you been troubled by a feeling of abdominal discomfort?	1	2	3	4	5	6	7
18.	How much of the time during the last two weeks have you been worried about the impact your liver disease has on your family?	1	2	3	4	5	6	7
19.	How much of the time during the last two weeks have you had mood swings?	1	2	3	4	5	6	7
20.	How much of the time during the last two weeks have you been unable to fall asleep at night?	1	2	3	4	5	6	7
21.	How often during the last two weeks have you had muscle cramps?	1	2	3	4	5	6	7
22.	How much of the time during the last two weeks have you been worried that your symptoms will develop into major problems?	1	2	3	4	5	6	7
23.	How much of the time during the last two weeks have you had a dry mouth?	1	2	3	4	5	6	7
24.	How much of the time during the last two weeks have you felt depressed?	1	2	3	4	5	6	7
25.	How much of the time during the last two weeks have you been worried about your condition getting worse?	1	2	3	4	5	6	7
26.	How much of the time during the last two weeks have you had problems concentrating?	1	2	3	4	5	6	7
27.	How much of the time have you been troubled by itching during the last two weeks?	1	2	3	4	5	6	7
28.	How much of the time during the last two weeks have you been worried about never feeling any better?	1	2	3	4	5	6	7
29.	How much of the time during the last two weeks have you been concerned about the availability of a liver if you need a liver transplant?	1	2	3	4	5	6	7

PHYSICAL HEALTH & COMORBIDITY

<< Components of FRAIL AAH Questionnaire >>

1.	How much of the time of	during the past 4 weel	ks did you feel tired? Pl	ease select one answe	r only.
	¹ All of the time ²	Most of the time ³	Some of the time 4	A little of the time 5	None of the time

- 2. By yourself and not using aids, do you have any difficulty walking up 10 steps without resting? 1 Yes • No
- 3. By yourself and not using aids, do you have any difficulty walking several hundred yards? 1 Yes • No

MEDICATIONS AND MEDICAL CONDITIONS

The next questions ask about your medication use and medical history. Please answer the best you can.

Antibiotics

1. Have you taken antibiotics in the past 12 months?

C1 Yes • No \rightarrow If NO skip to question # 2

hoa. How many courses of antibiotics have you taken during the past 12 months? A course usually lasts about one week, and does not count refills. courses

<<Ask i, ii, and iii for each course of antibiotics taken; use continuation sheet if needed>>

- i. What was your reason for taking this course of antibiotics? ² Treat an infection ¹ Prevent an infection
- ii. When did you start this course of antibiotics? ____/ (Month/Year)
- iii. When did you stop this course of antibiotics? ____/ (Month/Year)

Aspirin, NSAIDS, Statins, Beta Blockers

2.	Have you ever taken aspirin (examples: Bayer, Bufferin, Excedrin, Anacin, Ecotrin) at least 4 days per week
	for 3 months or longer?
-	

• No \rightarrow If NO skip to question # 3 1 Yes

 \Rightarrow a. How old were you when you started taking aspirin at least 4 days per week? _____ years old

b. Was it a baby or low-dose aspirin (162 mg or less)? 1 Yes \circ No \circ Don't know

c. Do you take aspirin at least 4 days per week now? ¹ Yes • No <</F NO>> d. When did you stop taking aspirin at least 4 days per week? _____ years old

3. Have you ever taken ibuprofen (examples: Motrin, Advil, Nuprin, Mediprin) at least 4 days per week for 3 months or longer? PI

Yes	0	No \rightarrow If NO skip to question # 4	

a. How old were you when you started taking ibuprofen at least 4 days per week? years old b. Do you take ibuprofen at least 4 days per week now? 1 Yes • No

< <if no="">></if>	c.	When did y	ou stop takir	ng ibuprofe	n at least 4	days per week?	years old
-----------------------	----	------------	---------------	-------------	--------------	----------------	-----------

4.	Have you ever	• taken acetaminophen (example: Tylenol) at least 4 days per week for 3 months or lon	iger?
E	Yes	• No \rightarrow If NO skip to question # 5	
6			

a. How old were you when you started taking acetaminophen at least 4 days per we	eek? years old
b. Do you take acetaminophen at least 4 days per week now? 1 Yes 0 No	

<</F NO>> c. When did you stop taking acetaminophen at least 4 days per week? _____ years old

- 5. Have you ever taken **Celebrex** at least **4 days per week** for **3 months** or longer?
- P^{1} ☐ Yes $^{\circ}$ $^{\circ}$ No \rightarrow If NO skip to question # 6
 - \Im a. How old were you when you **started** taking **Celebrex** at least **4 days per week**? _____ years old
 - b. Do you take **Celebrex** at least **4 days per week** now? ¹ Yes ⁰ No
 - <</IF NO>> c. When did you stop taking Celebrex at least 4 days per week? _____ years old
- - A. How old were you when you started taking other anti-inflammatory pain relievers at least 4 days per week? _____ years old
 - b. Do you take other anti-inflammatory pain relievers at least 4 days per week now? ¹ Yes ⁰ No
 <
 <

 <
- 7. Have you ever taken **beta blockers** (examples: Sectral, Tenormin, Zebeta, Lopressor, Corgard, Bystolic, Inderal LA, InnoPran XL) at least **4 days per week** for **3 months** or longer?

1 Yes

 $^{\circ}$ No \rightarrow If NO skip to question # 8

- A. How old were you when you started taking beta blockers at least 4 days per week? ______ years old
 b. Do you take beta blockers at least 4 days per week now? ¹ Yes ⁰ No
 <

 <
- **8.** Current Medications << Review Current Medication list with participant to verify what has been extracted from the medical chart with respect to drug name, drug dosage, and age started. >>
- 9. Has a doctor or health care provider ever told you that you had diabetes?
 - [⊥] Yes

 \circ \Box No \rightarrow If NO skip to question # 10

 \Rightarrow a. How old were you when a doctor first told you that you had diabetes? _____ years old

b. Did you do any of the following to monitor or treat your diabetes?

Check Yes or No for each item.	Yes	No
a. Use a home glucose test to monitor your insulin level?	1	0
b. Change your diet?	1	0
c. Take medication by mouth?	1	0
d. Take insulin by injection?	1	0

10. Have you ever had surgery to remove your [type of tissue]? Repeat for each type of tissue. If Yes,			How old were you when you
ask question about age when had surgery.	Yes	No	had this surgery?
a. Appendix	1	0	
b. Gall Bladder	1	0	
c. Gall Stones	1	0	
d. Stomach or part of your stomach	1	0	
e. Colon or rectum	1	0	
WOMEN ONLY:			
f. Breast (mastectomy)	1	0 🗌	
g. Uterus (hysterectomy)	1	0	
h. Ovaries (oophorectomy)	1	0	

11. Have you ever had a transjugular intrahepatic portosystemic shunt (TIPS)? TIPS is a non-surgical procedure to create new connections between two blood vessels in your liver.

Solution f a. How old were you when you had this procedure? _____ years old

12. Have you ever had a distal splenorenal shunt (DSRS)? DSRS is a surgical procedure where the vein from the spleen (called the splenic vein) is detached from the portal vein (the vein that carries blood from the digestive organs to the liver) and reattached to the left kidney (renal) vein.

P1 Yes • No \rightarrow If NO skip to question # 13

arphia. How old were you when you had this procedure? _____ years old

ANTHROPOMETRY

The following questions ask about your physical development.

1. What is your current height? _____ Feet _____ Inches

2. What was your maximum height as an adult? _____ Feet _____ Inches

<< The next 2 questions are Components of the FRAIL AAH Questionnaire >>

- 3. How much do you currently weigh with your clothes on but without shoes? _____ Pounds
- 4. One year ago in (___/___ Month/Year), how much did you weigh with your clothes on but without shoes? Pounds
- 5. Compared with other [insert boys/men or girls/women] in the same age range, when you were [age range], were you considered: (Check one box for each gae range, and ask about average weight in gae range.)

	15-19 years old	20-29 years old	30-39 years old	40-49 years old	50-59 years old	60-69 years old	70+ years old
Very Thin	1	1	1	1	1	1	1
Somewhat Thin	2	2	2	2	2	2	2
Average Weight	3	3	3	3	3	3	3
Somewhat Heavy	4	4	4	4	4	4	4
Very Heavy	5	5	5	5	5	5	5
Not Applicable	8	8	8	8	8	8	8
What was your average weight in this age range?	lbs.	lbs.	lbs.	lbs.	lbs.	lbs.	lbs.

TOBACCO

	The next questions ask about your use of tobacco. Please answer to the best of your ability.
1.	Have you ever smoked at least one cigarette a day for 6 months or longer? ¹ Yes \circ No \rightarrow If NO skip to next section – ALCOHOL
2.	How old were you when you first started smoking cigarettes daily ? years old
3.	During the time you smoked, how many cigarettes did you usually smoke each day? cigarettes per day
4.	How many years have you (or did you use) smoke at least one cigarette a day? years
5.	Do you smoke cigarettes now? ¹ Yes ⁰ No <> a. How old were you when you quit smoking cigarettes? years old

ALCOHOL

<<Alcohol Use Disorders Identification Test for Alcohol Consumption (AUDIT-C)>>

The last questions ask about your use of alcohol. Your answers will remain confidential so please be honest.

Now I am going to ask you some questions about your use of alcoholic beverages **during this past year**. One drink of alcohol is a 12-ounce bottle or can of beer, an 8-ounce bottle or can of malt liquor, a 12-ounce wine cooler, a 5-ounce glass of wine, a 1½ ounce shot of liquor, or a mixed drink containing 1½ ounces of liquor, such as gin, vodka, rum, or whisky.

- 1. How often do you have a drink containing alcohol?
 - ° Never → If Never the interview is completed
 - ¹ Monthly or less
 - ² 2 to 4 times a month
 - ³ 2 to 3 times a week
 - 4 dor more times a week
- 2. How many drinks containing alcohol do you have on a typical day when you are drinking?
 - 1 or 2
 - ¹ 3 or 4
 - ² 5 or 6
 - ³7, 8, or 9
 - 10 or more
- 3. How often do you have six or more drinks on one occasion?
 - Never
 - ¹ Less than monthly
 - ² Monthly
 - ³ Weekly
 - ⁴ Daily or almost daily

END OF INTERVIEWER-ADMINISTERED QUESTIONNAIRE

Thank you for taking the time to complete the interview. This information is vitally important to our study and we greatly appreciate your contributions.

INTERVIEWER'S REMARKS

1.	Participant ID
2.	Interviewer (Initials)
3.	Participant's sex ¹ Male ² Female
4.	Participant's date of birth Month Day Year (Current Age:)
5.	Date of Interview Month Day Year
6.	Interview Start Time: (Hour: Minutes [24-hour time])
7.	Interview End Time: (Hour: Minutes [24-hour time])
8.	The interview included: (Check all boxes that apply.) ¹ The participant only ² A spouse or partner ³ Another family member ⁴ Another person (please specify)
9.	The participant's cooperation was: (Check one box only.) ¹ Excellent ² Very Good ³ Good ⁴ Fair ⁵ Poor
10.	The quality of the interview is: (Check one box only.) ¹ Excellent ² Generally reliable ³ Questionable ⁴ Unreliable
Sig	nature of Clinical Research Staff who administered questionnaire Date

Signature of Clinical Research Staff who administered questionnaire

